1.8 APPROVALS, DATA USE AGREEMENTS, AND CONTRACTS

The following will occur for this study.

Institutional Review Board (IRB) Approval

In compliance with GVSU and MDHHS policy, prior to data collection we will obtain IRB approval from the following.

1. GVSU
2. MDHHS

We will update the IRBs as changes occur over the course of the study.

Data Use Agreements (DUA)

In compliance with GVSU policy, we will collaborate with the Center for Scholarly and Creative Excellence to fully execute the following DUAs prior to data collection or use.

1. Between the university and MDHHS for: MDS (2017-2021), administrative (2018), Continuous Quality Assessment Review (CQAR) scores (2015-2017), and cost (2020) data
2. Between the university and the 18 sites and CIM for data from EHRs MDS, person centered service plan (PSCP), and progress notes (PNs) data (2017-21).

We will update the DUAs as changes occur over the course of the study.

Contracts to be Execute

In compliance with GVSU policy, we will collaborate with the Center for Scholarly and Creative Excellence to fully execute the following contracts prior to working with a site or data analysis by the statistician.

1. Between the university and the 18 site prior to initiating the project (role and responsibilities; training; tasks; duties; timelines; actions; and use of CAPABLE with fidelity to the intervention).
2. Between the university and the biostatistician prior to data analysis.

We will update the contracts as changes occur over the course of the study.

1.9 ORGANIZATIONS ASSOCIATED WITH THE STUDY

NIA The National Institutes of Aging funded the project (NIA 1 R15 AG058193-01A1). As such, for this study, all requirements (i.e., privacy, confidentiality, Health Insurance Portability and Accountability Act (HIPAA), IRB, budget, report, dissemination, data sharing, protocol, etc.) will be met through execution and implementation of the Notice of Award (NOA) agreement with the university.

CMS The Center for Medicare and Medicaid Services is the oversight organization of MDHHS. As such, for this study, all requirements (i.e., privacy, confidentiality, HIPAA, etc.) will be met through execution and implementation of the MDHHS IRB and DUA.

MDHHS The Michigan Department of Health and Human Services (MDHHS) is the oversight organization of all Medicaid programs for the State of Michigan, and as such, contracts with each of the waiver sites to manage, hire, or contract employees, and provide care to beneficiaries in the waiver program. As an oversight organization, MDHHS collects administrative, CQAR, and beneficiary data and has access to all current and past data of this nature. We will execute an IRB and DUA with MDHHS to perform this study.

Sites Home and Community Based Services Provider waiver program sites are under contract with State of MI MDHHS to manage, hire or contract employees, and provide care to beneficiaries in the waiver program. We will execute a contract and DUA with each site that agrees to participate to perform this study. Deployment will occur in a staged manner, with 2—4 sites each month until all are deployed.

CIM Center for Information Management (CIM) is under contract with MDHHS and 18 sites (20 years) to house and manage the EHR and billing software for the State of MI Medicaid waiver program. This platform contains beneficiary level data for all Medicaid beneficiaries in the waiver program where our study will occur.

The website (www.ciminc.com/) provides a description of CIM's mission and purpose; and contains a statement of HIPAA compliance, required by CMS and MDHSS. We will obtain a DUA. The following will occur.

1. De-identified data on beneficiaries outcomes from care by clinicians trained in CAPABLE at sites who do not opt-out will be obtained from CIM.
2. Data transfer to the university (PI/PM) will be electronic through a CIM data secure encrypted portal as the data will be de-identified.
3. Data would be downloaded by PI/PM on encrypted jump drives; and stored in a locked file cabinet in GVSU CHS Room 323 (Research Center) with a door that is locked at all times and only accessed by faculty approved to use the room. Only the PI/PM have access to the locked files cabinet.
4. Clinicians (RNs/SWs/OTs) and IFs, who are also the supervisors of the clinicians at the sites, already have access to all identifiable CIM data in the EHR (Medicaid beneficiary data) to provide usual care.
5. Clinicians (RNs/SWs/OTs) and IFs will not use the data the university (PI/PM) obtained from CIM.

1.10 EVIDENCE-BASED INTERVENTION: CAPABLE

A multi-component model of care, CAPABLE, was designed to reduce the effect of problems with physical function among low-income older adults living at home by addressing an individual's capabilities and the home environment.¹¹⁻¹² CAPABLE is a 16-week structured program delivered by OTs who conduct 6 home visits and provide assistive devices, RNs who conduct 4 home visits, and a handyman who provides home alterations (i.e., installs devices, environmental modifications, and home repair).¹⁵⁻¹⁹ CAPABLE is interdisciplinary team provides consultation with older adults to help them identify daily activity goals (e.g., taking a shower, walking to the bathroom), evaluate barriers to achieving those goals, and attain outcomes collaboratively.^{11, 18} The OT assists older adults to carryout ADLs, instrumental activities of daily living (IADLs) and discretionary activities that are challenging at home such as functional mobility, meal preparation, bathing, and dressing. The RN targets underlying issues that influence ADLs, IADLs, and discretionary activities at home, such as pain reduction, improvement in mood, fall prevention, medication review and management, primary care physician communication, incontinence management, sexual health, and smoking cessation. The Disablement Process,²⁰ Life Span Theory of Control,²¹ and Szanton-Gill Resilience Model²² underpin CAPABLE. CAPABLE has demonstrated a 49% reduction in the number of ADL difficulties; and 75% of beneficiaries improved their level of ADL performance from baseline to follow-up at 5-months.¹⁷

Prior Work In prior work of this team, Normalization Process Theory²³ underpinned identification of six adaptations of CAPABLE to fit the waiver population and setting. This included: assigning a team leader (RN), adding SWs to address social and emotional needs, utilizing an RN to conduct medication review rather than a pharmacist, flexibility in the number and type of home visits delivered and the number of weeks (extended to 32 weeks) CAPABLE was provided, care coordinated among the RN, OT, and SW face-to-face, by phone, Skype, or email with the supervisor. A toolkit that included the 12 most common aging-in-place problems (i.e., falls, balance and strength exercises) was provided to beneficiaries; and home alterations were done when medically necessary (Medicaid rule).

1.11 IMPLEMENTATION STRATEGIES

Strategies deployed in this project to implement CAPABLE are shown in the figure; and described below.

Pre-Implementation Strategies

Relationship Building Informal relationships (collaborative work/meetings) are in place between sites and the university team from decades of prior work; and will continue to be built. Formal relationships (contracts) with MDHHS, CIM, and sites will delineate responsibilities and actions for this project.

Readiness to implement and **leadership** of the site and **attitude** of clinicians will be collected.

Champion Coalition Building IFs are clinicians with exemplary clinical practice and supervisory experience and are expected to be early adopters.

MiCAP Implementation Strategies Deployed in this Project and Domains Affected by Strategies							
DOMAIN AFFECTED BY STRATEGY	MiCAP IMPLEMENTATION STRATEGIES DEPLOYED IN THIS PROJECT						
	Pre-implementation		Implementation: Education & Training			Centralize Oversight	Audit & Feedback
	Organization readiness	Build IF Coalition	IF Champions	Train clinicians	Develop clinical teams	EF	Implementation intervention outcomes
Definition	Aspects of an organization determine readiness to implement ²²	IFs coalition to share implementation knowledge ²²	Dynamic interactive training via varying learning methods; & supervision focused on implementation ²²	Training to conduct intervention	Develop/implement teams of clinicians who meet, reflect, & share learnings ²²	Makes things easier for others: support to change attitudes, habits, skills, way of thinking & working ²²	Collect & summarize clinical performance & monitor, evaluate, modify clinician behavior ²²
Actors	[name], [name], waiver clinician	IF, research team	Research team for IF	IF for clinicians	IF, clinicians	EF	[name], [name], IF, EF
Actions	Administer tools; analyze results	Online Bb forum to build capacity; share best implementation strategies	Identify and train train-the-trainers/IF; Pre/post-test	Train clinicians; Pre/post-test; Remediate	IF leads interdisciplinary coordination; feedback on implementation/ Intervention	Assistance to IF (Arm 2)	Monitor Bb & EHR; SIC (scorecard); low adopters moved to Arm 1/2 per protocol
Target of the action	Site	IFs	IFs	Clinicians	Clinicians	IF	Clinicians
Temporality	3-months after funded		When starting implementation			1-month after implement	1 week after CAPABLE & ongoing
Dose	Surveys completed Baseline	1-hour discussion weekly	2-hr Bb and 2-hr training; Remediate prn	4-hr online Bb and 4-hr in person training	Meet weekly 1-hour	Weekly for 30 minutes to 1 hour until issues resolved	Weekly results to scorecard in Bb and IF reviews with clinicians; EF reviews with IF
Outcomes affected	Acceptability, readiness	Acceptability	Adoption, sustainability			Adoption, sustainability	Adoption, sustainability, outcomes

Implementation Strategies

Training Clinicians (RNs/OTs/SWs) will be trained in CAPABLE principles, approaches, techniques, and documentation (4-6 hours; pre/post-test).

Interdisciplinary coordination (RNs/OTs/SWs) will be led by IFs, focused on care coordination to promote teamwork; using brainstorming/problem solving care issues to support beneficiary goal attainment.

IFs will **facilitate** and EFs will provide **centralized oversight** for Arm 2 IFs. An IF at each site and an EF (from prior work and were trained and early adopters of CAPABLE) will be selected by the PI and will be trained (2 hours; and take a pre/post-test) in facilitation. IFs will encourage clinicians to complete CAPABLE training; and for those trained, provide feedback; facilitate fidelity to CAPABLE; and conduct remediation as needed from Month 1 through 9. EF will facilitate IF's work with clinicians trained in CAPABLE and assistance will be tailored to a site's needs.

Audit and Feedback on CAPABLE and implementation strategy fidelity data will be provided to IFs to be used to provide feedback to clinicians and develop an improvement plan as needed. The EF will use the data to facilitate IFs and develop an improvement plan as needed.

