1.3 SPECIFIC AIMS

The **specific aims** are as follows.

Aim A1 To test the effects of MiCAP with IF alone versus MiCAP with IF+EF with respect to the site-level outcomes of adoption and sustainability (**primary**) and beneficiary-level outcomes of ADL/IADLs, pain, depression, falls, emergency department (ED) visits and hospitalizations (**secondary**) over the next 12 months.

Aim A2 Mechanism-of-action To determine whether the effects of EF+IF versus IF on primary outcomes are mediated by clinician attitude or self-efficacy at 9 months.

Aim A3 To benchmark the effects of IF and EF+IF on beneficiary outcomes following implementation as compared to pre-intervention.

Exploratory Aim A4 To compare the primary and secondary outcomes within 12 months, potential mediators at 9 months, and baseline leadership and readiness for sites with SIC of >50% versus sites with SIC \leq 50% at 6 months in each arm.

Exploratory Aim A5 To explore whether baseline site leadership and readiness moderate the impact of EF+IF compared to IF on primary and secondary outcomes within 12 months in order to determine which sites may require facilitation that is more intensive.

Exploratory Aim A6 To evaluate clinician satisfaction at 1 month, and the cost of implementation and policy impact for IF and IF+EF at 12 months.

The National Institutes of Health (NIH) defines Implementation Science (IS) as the process of applying evidence to the treatment or prevention of human disease.¹⁹⁻²⁰ A scientific study of methods to promote uptake of evidence into routine care to improve quality and effectiveness of healthcare through the study of influences on clinician and organizational behavior.²¹ This study is significant because it addresses testing of multimodal implementation strategies of an evidence-based intervention (CAPABLE) in a Medicaid setting to improve the quality and effectiveness of a waiver.

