1.5 SAMPLE

The sample includes the following groups:

1. Sites: The 18 Medicaid Waiver program sites in the State of MI.
2. Clinicians: The 575 RNs/OTs/SWs employed by the site to provide care to beneficiaries.
3. Beneficiaries: The 15,000 Medicaid beneficiaries who are recipients of care in the site.

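### The strategy table has low adopters changing arm, but no move rule is given, sites are randomised once, and the analysis does not say that trial arm means arm as randomised

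*Combined protocol and SAP*

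**What the plan says.** In the MiCAP table of section 1.11, the Actions cell of the Audit & Feedback column ends with "low adopters moved to Arm 1/2 per protocol". The timing given for that column is "1 week after CAPABLE & ongoing". Its definition is "Collect & summarize clinical performance & monitor, evaluate, modify clinician behavior" and its target row names clinicians, yet the same Actions cell names the SIC, which is scored by site.

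Other parts of the plan bear on this:

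- **1.16** randomises by site: pairs matched on size and CQAR score, one coin flip, no later step.
- **1.11, audit and feedback text**, provides feedback to clinicians and improvement plans. For the external facilitator it says "The EF will use the data to facilitate IFs and develop an improvement plan as needed". It mentions no change of arm.
- **1.20** covers only withdrawal and discontinuation.
- **1.3, Aim A1**, is "To test the effects of MiCAP with IF alone versus MiCAP with IF+EF".
- **1.3 and 1.14, Aim A4**, compare "sites with SIC of >50% versus sites with SIC" at or below that level at 6 months, within each arm. This is the only adoption cut-off in the text, and it is not linked to a move.
- **1.14** bases the formal test on the coefficient of trial arm. It lists that variable next to the randomisation variables but does not define it.
- **1.15** sizes a fixed comparison of 9 with 9 sites.

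**The concern.** Monthly SIC is one of the primary outcome series. If a low SIC leads to a change of arm, the exposure being compared depends on the outcome used to compare it. The text does not say who moves. Arms exist only by site, and external facilitation is given to the Arm 2 internal facilitator, so it is unclear how a single clinician could change arm.

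There are two possible readings, and they estimate different things. If the move is not part of the strategy, the as-randomised analysis keeps its type I error but estimates a diluted version of Aim A1. If the move is intended, the same analysis validly compares strategies that include it, but neither Aim A1 nor 1.15 describes that comparison. The distinction has a practical consequence: 1.15 says that a non-significant estimate will be used to power the next trial, so its readers must know which comparison it estimates.

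**Working it through.** **Inputs from 1.14 and 1.15.** 9 sites per arm; 11 monthly records (months 2 to 12 in the 1.13 table); correlation 0.7; detectable effect 1.2 SD.

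**Assumed.** Two-sided 5%, because 1.15 states neither alpha nor power. The k lowest Arm 1 sites move after month 6 (borrowed from Aim A4), so 6 of 11 records follow the move. Each moved site takes on the full EF effect at once. Pairing and covariates are ignored.

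**Step 1: reproduce 1.2.**

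- Variance of a site's time-average = (1 + 10 × 0.7)/11 = 0.727, so SD = 0.85.
- Standard error of the arm difference = √(2/9 × 0.727) = 0.402.
- The non-central t with 16 df at 1.2/0.402 gives 80.0% power. The plan's figure holds.

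**Step 2: dilution, analysed as randomised.** Difference = 1.2 × (1 − k/9 × 6/11).

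- k = 1: 1.2 × (1 − 0.0606) = 1.127
- k = 3: 1.2 × (1 − 0.1818) = 0.982
- k = 5: 1.2 × (1 − 0.3030) = 0.836
- Three swapped each way: 1.2 × (1 − 6/9 × 6/11) = 0.764

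Power is shown on two bases. The first holds the SD at 0.85. The second simulates the moves (40,000 replicates per scenario, t-test on site time-averages, sites ranked on month 6 or on the mean of months 2 to 6). Lifting the lowest sites narrows the spread: with month-6 ranking the SD falls to 0.81, 0.78 and 0.77 for k = 1, 3 and 5. Swapping three each way widens it to 0.92.

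| Sites moved after month 6 | Difference (original SD) | Power, fixed SD | Power, simulated |
|---|---|---|---|
| none | 1.20 | 80% | 80% |
| 1 from Arm 1 | 1.13 | 75% | about 78% |
| 3 from Arm 1 | 0.98 | 63% | 70-71% |
| 5 from Arm 1 | 0.84 | 50% | 57-59% |
| 3 each way | 0.76 | 43% | 37-38% |

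Type I error in the as-randomised analysis stayed at 4.9-5.2%.

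**Step 3: sensitivity with 3 sites moved (simulated power).**

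- After month 3: 1.2 × (1 − 3/9 × 9/11) = 0.87, about 62%.
- After month 9: 1.2 × (1 − 3/9 × 3/11) = 1.09, about 76%.
- After month 6 with half the EF effect: 1.2 × (1 − 0.5 × 3/9 × 6/11) = 1.09, about 76%.
- IF-tool series of 9 records, taking 1.2 there too: 1.2 × (1 − 3/9 × 3/9) = 1.07, or 1.2 × (1 − 3/9 × 4/9) = 1.02, for 3 or 4 records after month 6.

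**Step 4: if clinicians move instead.** Section 1.5 gives the clinician sample as "The 575 RNs/OTs/SWs employed by the site to provide care to beneficiaries", and 575/18 is about 32 per site. Suppose the site outcome is proportional to the share f of Arm 1 clinicians exposed from month 7. Then the difference is 1.2 × (1 − f × 6/11). For f = 10%, 25% and 50% it is 1.13, 1.04 and 0.87, with fixed-SD power of about 75%, 68% and 53%. Compare these with the fixed-SD column above, not the simulated one.

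**Step 5: if trial arm were taken as the final arm.** The plan does not propose this. With no true effect and the 3 lowest Arm 1 sites counted in Arm 2, the contrast is biased by −0.54 to −0.62 SD, and false rejection is 23-30%, depending on the ranking rule.

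The training-fidelity model and the log-rank and Cox analyses were not examined.

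**The case against.** The concern rests on one cell of a summary table. No prose section mentions a move, and the cell refers to a protocol rule that may sit in an attachment listed in 1.27 and not supplied. That stands: the text does not show that any site will be moved. But even if a rule exists elsewhere, 1.14, 1.15 and 1.16 make no allowance for it, so the passages still need reconciling.

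Trial arm is most naturally read as the randomised arm, given the wording of 1.14 and 1.15. That also stands, and it is why the final-arm figures are a warning about an unproposed analysis, not a prediction. One sentence in 1.14 would settle the matter.

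The magnitudes depend on assumed moves. An immediate full effect is probably too strong for a score that accumulates, such as the SIC stage count; with half the effect and three sites moved, about 4 points of power are lost (80% to 76%). The clinician scenario rests on a proportionality rule that the plan does not contain. These limits weaken the figures but do not remove the textual conflict.

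Finally, stepping up support may be intended, since Aim A5 asks which sites need more intensive facilitation. In that case the move is legitimate, but the aim and the power statement must describe it.

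**Conclusion.** The concern holds and should be fixed. Current text provides for moving low adopters between arms, which conflicts with a single site-level randomisation and a fixed 9 v 9 comparison. Confidence is high on the conflict itself. The size is illustrative, because the plan gives no number, month or direction of moves. For 1 to 5 Arm 1 sites moved after month 6, the as-randomised contrast falls from 1.20 to between 1.13 and 0.84 SD, and simulated power from 80% to between about 78% and 57%. With no moves there is no loss. As randomised, the test remains valid; what is unclear is which comparison it estimates.

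**What to change.** Reconcile the Audit & Feedback cell in 1.11 with 1.16, in one of three ways:

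1. Delete the clause.
2. Defer any change of arm until after the month-12 SIC, relying until then on the improvement plans already in 1.11.
3. If moves are intended, write the rule into 1.16 (unit, trigger, cut-off, month, direction), state that the comparison is then of strategies that include the move, and restate Aim A1 and 1.15 to match.

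Whichever is chosen, state in 1.14 that trial arm in every model is the arm assigned in 1.16, and that any moved site is reported and analysed in its randomised arm.

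The cost is wording in 1.11 and 1.14, plus 1.3, 1.15 and 1.16 under the third option. The one real trade-off is that under the first two options, low-adopting Arm 1 sites receive no EF support before month 12.

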Testing will occur in a 3-year community-based participatory research¹³ with Hybrid-3¹⁴⁻¹⁵ mixed method trial design.¹⁶⁻¹⁸ With rolling enrollment, sites will be randomized to MiCAP with IF or MiCAP with IF+EF and baseline assessments of the characteristics of sites and clinicians will be completed. CAPABLE will be provided to beneficiaries. Clinicians (RNs/OTs/SWs) and IFs will be trained in CAPABLE. IFs and EFs will be trained in facilitation techniques. Post-implementation data, site Stages of Implementation Completion (SIC), and clinician satisfaction will be collected; an implementation fidelity checklist (including IF/EF fidelity) will be completed monthly. Clinician attitude and self-efficacy will be measured at baseline and 9 months. Beneficiary level data will be collected during usual care and includes assessment prior to and after CAPABLE and any assessments that occurred between the two time points.

The *significance* of this project is in the use of the evidence-based model, CAPABLE, in an underfunded Statewide Medicaid environment, where change is difficult to attain. This work will impact implementation science by testing two approaches to implementation of an evidence-based intervention to improve outcomes among older adults in a Medicaid waiver program. This natural setting approach has high generalizability for waiver sites, as we learn what intensity of implementation strategies is needed to adopt and sustain evidence, potentially transforming programs of care for our nation's most vulnerable older adults who are aging-in-place. This study is also significant as it addresses a critical barrier to implementation of evidence-based interventions to improve function in older adults living in the community to age-in-place (CAPABLE). The National Institute on Aging focuses on ways to improve function once considered an inevitable part of aging. Likewise, the American Association of Retired Persons, National Aging in Place Council, and National Association of Area Agencies on Aging have aging-in-place as a priority. Evidence suggest 90% of older adults prefer to age-in-place; yet a gap exists between their desire and ability.²⁹ Thus, further testing of efficacy of an intervention (CAPABLE) in a Medicaid waiver population will fill a gap in science and build evidence.

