We will utilize implementation strategies²² refined in prior work (MiCAP; Hartford/Hillman/CMS) where we trained clinicians (N=34), modified the EHR, and provided CAPABLE for beneficiaries (N=270). We extend our work and train all RNs, OTs, and SWs (N=575) in the 18 waiver sites in MI to implement the CAPABLE model of care for all Medicaid waiver beneficiaries (N=15,000). Guided by site managers, our team will select and train Internal Facilitators (IFs), who are supervisors/employees that work for the waiver site, to conduct facilitation at each site as “Champions”. We will utilize waiver employees as the External Facilitators (EFs), who were early adopters of CAPABLE in our prior work, as “Super-Champions” for Arm 2.

Further, we focus on a topic of particular IS import: sustainability of implementation efforts.²³⁻²⁶ In a recent scoping review of 62 trials and 41 reports in the field of knowledge translation, few studies focused on sustaining interventions.²⁷ Without sustainment, true practice change may not occur and healthcare outcomes may not improve. Further, we will be one of the first to examine implementation strategy (MiCAP) mechanisms of action - awareness, commitment, confidence, and trust - identified in the work of Abramowicz and colleagues in 2016,²⁸ while implementing a complex intervention (CAPABLE).

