1.16 RANDOMIZATION

Randomization for this study occurs at the site level. Sites will be randomized by the PM, to **Arm 1** (MiCAP with IF) or **Arm 2** (MiCAP with IF+EF) using the following steps.

Step 1: Data on site size (number of beneficiaries [patients]) and Clinical Quality Assessment Review (CQAR) scores will be obtained.

Step 2: We will block sites in pairs with similar size and CQAR scores, and flip a coin to determine **Arm 1** or **Arm 2** assignment for study.

The PM will maintain a confidential file documenting study Arm by site. Only the PI/PM will know Arm assignment by site.

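### The principal investigator selects each site's internal facilitator and knows its arm, and nothing requires the facilitator to be named before the pair is randomised

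*Combined protocol and SAP*

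**What the plan says.** **Who chooses.** Section 1.11 has the IF at each site, and the external facilitator (EF), chosen by the principal investigator (PI): "will be selected by the PI and will be trained (2 hours". Section 1.3 describes a shared choice: "Guided by site managers, our team will select and train Internal Facilitators (IFs". Section 1.1 limits the IF to a supervisor at the site. Section 1.11 adds broad expectations: strong clinical practice, a supervisory background and likely early adoption.

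**Who knows the arm.** The project manager (PM) randomises. Section 1.16 gives the method: "We will block sites in pairs with similar size and CQAR scores, and flip a coin to determine". It then says: "Only the PI/PM will know Arm assignment by site".

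**When the IF is chosen.** No section orders this step relative to the flip. Section 1.2 says: "With rolling enrollment, sites will be randomized to MiCAP with IF or MiCAP with IF+EF and baseline assessments". It mentions IF training later but not IF selection. The strategy table in Section 1.11 lists the action "Identify and train train-the-trainers/IF; Pre/post-test", apparently under the timing "When starting implementation".

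**What the IF does.** The IF leads implementation at the site in both arms (Section 1.1). Under Section 1.13, research assistants telephone the IFs, and the data collection table there has SIC coming from the IFs in months 2 to 12.

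**What the primary model adjusts for.** Section 1.14, Aim A1, lists arm, site size, CQAR score and time.

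**The concern.** Randomising sites protects the comparison only for features already fixed when the coin is flipped. The IF may not be one of them. If the IF is chosen afterwards by someone who knows the arm, the choice can depend on the arm, even without intent.

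The IF matters twice: as the person who leads the work that adoption and sustainability measure, and as the informant for SIC, one of the primary measures. Better-placed IFs in the IF+EF arm would inflate the apparent EF effect. Better-placed IFs in the IF-alone arm, perhaps to make up for the missing EF, would hide a real one. Section 1.15 says that, if significance is not reached, the effect estimate will be used to power a later trial, so a distorted estimate would carry forward even without a significant result.

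**Working it through.** The point is about procedure and rests on no figure in the plan. The check is to set the statements side by side.

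1. *Is the chooser unmasked?* Yes. Section 1.11 names the PI as selecting the IF, and Section 1.16 names the PI among the two people who know the arm.

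2. *Is selection required to come before the flip?* No section says so. The two steps in Section 1.16 (obtain size and CQAR data; pair and flip) do not mention the IF.

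3. *Which way does the timing evidence point?*
   - Towards later selection: the strategy table's action of identifying and training IFs appears to fall under the start of implementation. The table's layout is broken in the text, so this is the likely reading and not a certain one.
   - Towards earlier selection: the same table puts building the IF coalition under pre-implementation, and the Section 1.13 table has IFs consenting and completing the leadership (ILS) and readiness (ORCA) surveys at month 0.
   - Neutral: Section 1.2 does not mention selection, and month 0 is nowhere tied to the date of the flip.

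   The documents settle neither order, so selection after the flip is permitted.

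4. *Does anything else remove the PI's discretion?* Site-manager guidance (Section 1.3), the supervisor requirement (Section 1.1) and the expectations in Section 1.11 narrow it. None of them masks the chooser, fixes the date, or gives a rule for choosing between two eligible supervisors.

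5. *Would the analysis absorb a difference in IFs?* Pairing uses size and CQAR score, and the primary model adjusts for the same two. ILS and ORCA enter only exploratory Aims A4 and A5.

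6. *How precise is the primary comparison?* Inputs from Section 1.15: 9 sites per arm, 11 repeated measures, correlation 0.7.
   - Variance factor for the time-averaged mean: (1 + 10 × 0.7)/11 = 0.727.
   - Standard error of the arm difference: √((2/9) × 0.727) = 0.402 SD.
   - Detectable difference, non-central t with 16 df: 1.20 SD, which matches the plan's figure of about 1.2. Two-sided 5% and 80% power are assumed, because Section 1.15 states neither.

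   This confirms the plan's arithmetic and shows how few sites carry the comparison. It says nothing about how large an IF-related difference might be.

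**The case against.** The strongest reply is that the plan leaves less room for arm-aware choice than Sections 1.11 and 1.16 suggest when read alone. Site managers guide the selection, the IF must already supervise at that site, and the same expectations apply in both arms. IFs appear in pre-implementation activity and in the month 0 data. That much stands: discretion is narrowed and the timing evidence is mixed. It does not close the gap, because neither the order nor masking is stated.

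Three stronger readings are tempting, and the documents do not support them.

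- *A reader might infer that Section 1.2 prescribes randomising first and choosing IFs afterwards.* That text is a loose summary. It joins randomisation and baseline assessment with no stated order and mentions CAPABLE delivery before training, although Section 1.7 includes beneficiaries cared for by trained clinicians.
- *A reader might infer that a difference in IFs could never be separated from the EF effect.* IF demographics, survey scores, training tests and monthly activity are collected, so an imbalance could be described. Eighteen sites leave little room for adjustment, so hard to separate is the accurate description.
- *A reader might want a false-positive rate.* One can be computed for any assumed shift, but the documents give no shift and no direction. Such a rate would describe the assumption and not this trial.

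**Conclusion.** The concern holds as a gap in procedure. The plan lets a person who knows the arm choose the individual who leads implementation and reports SIC, and it does not require that choice to be fixed before randomisation. This is an unguarded risk. The documents do not show that any IF was or will be chosen with the arm in view, and they give no size for the effect.

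The conclusion rests on the absence of an ordering rule anywhere in the plan. It does not depend on the column reading of the strategy table, which only makes later selection more likely. It is more than a missing detail because there are only 9 sites per arm, the primary model has no IF covariate, and the remedy is nearly free.

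**What to change.** In Sections 1.11 and 1.16, state that each site's IF is named and recorded, with a date, before that site's pair is randomised. The signed site contract is a natural place: Section 1.8 already requires one before the project starts at a site and has it cover roles and responsibilities. Because the plan does not place the contract relative to the flip, the text should say that the record comes first.

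Also require that any later change of IF is logged with its date and reason, and that the site stays in its randomised arm.

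The cost is small. Both sites of a pair must name an IF before the coin is flipped, which may delay a pair under rolling enrolment. Sample size, outcomes and models do not change. There is no need to complete ILS and ORCA before randomisation: ORCA alone has 115 or 124 items depending on the version, and waiting for clinicians at both sites of a pair would be a much heavier demand than this risk calls for.
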